2. DATA AND METHODS

2.1 Research Team and Reflexivity

This study was a partnership between researchers, educators, and environmental protection staff at the University of Alabama at Birmingham (UAB), the University of California, San Francisco (UCSF), and the Sitka Tribe of Alaska (STA). The community-academic partnership was initiated in 2016 when academic partners were invited to support the efforts of a Tribe-school district partnership in Sitka and a tribally led environmental monitoring program. The partnership involves shellfish toxin testing and modeling and K-12 educational programming to promote cultural, environmental, and health literacy and increase awareness of shellfish poisoning risk reduction strategies and STA risk reduction resources. The intervention evaluated in this study is a new education program for middle school students. This work is community co-led and participatory (Key et al., 2019), reflects reflexive research ethics principles (Cordner et al., 2016), and follows best practices for co-created community engagement in oceans and human health research (Carson et al., 2022). Community-based participatory research offers a model for fostering trust, reciprocity, and long-term collaboration with Indigenous communities (Manson et al., 2004). The research instruments used in this study were developed collaboratively by members of the author team with academic and STA affiliations. Surveys were conducted by coauthors implementing the education program in Sitka, Hoonah, and Juneau and respectively affiliated with STA, the Hoonah Indian Association, and the Central Council of the Tlingit and Haida Indian Tribes of Alaska. Interviews, across communities, were conducted by coauthors with STA and UAB affiliations. This research received human subjects research approval from the University of Alabama at Birmingham Institutional Review Board (IRB protocol number 300006786). In reporting, we draw on three guidelines, including criteria specific to health research with Indigenous Peoples (Hurria et al., 2019), environmental education

research (Smith-Sebasto, 2000), and group-based behavior-change interventions (Borek et al., 2015). We present consolidated criteria for strengthening reporting of health research involving Indigenous Peoples in appendix 1 (Hurria et al., 2019) and relevant items from the other two guidelines in this methods section.

2.2 Middle School Education Program

The middle school education program that this study evaluates teaches participants about traditional knowledge and shellfish harvesting practices in Southeast Alaska, risks posed by shellfish toxins, and risk reduction strategies. The program was designed by STA, run by education and environmental coordinators working for STA, the Hoonah Indian Association, and the Central Council of the Tlingit and Haida Indian Tribes of Alaska, and featured guest speakers, such as staff scientists responsible for shellfish toxin testing and tribal members with expertise in local knowledge and traditional knowledge (Roland, Kohlhoff, Lanphier, Yazzie, et al., 2024). The program was initially implemented only in a middle school in Sitka and was expanded to schools in Hoonah and Juneau in response to Tribes' interest. The semester-long, one hour program took place weekly, either as an after-school program or during school hours as a non-graded elective, depending on the structure most feasible for schools. Lessons offered participants hands-on learning such as experience with laboratory techniques, microscopy, plankton tows, and shellfish harvesting. The program was divided into two units: the first focused on harmful algal blooms and paralytic shellfish poisoning and the second focused on intertidal zones and shellfish harvesting. Research activities included pre- and post-program interviews and surveys and a follow-up survey one year after participation. Pre- and post-program surveys were the primary outcome measure of the clinical trial, and pre- and post-program interviews and the one year post-program survey were secondary measures.

The program was designed with the TPB in mind and especially targeted control beliefs. The program aimed to influence behavioral beliefs by educating students about shellfish harvesting through hands-on, place-based learning; normative beliefs by emphasizing that harvesting with parents or guardians is customary; control beliefs by highlighting exposure risk reduction strategies and tribal paralytic shellfish poisoning prevention resources; and, ultimately, behavioral intentions through shifting behavioral, normative, and control beliefs.

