2.4 Survey Design

A five-point (1-5) Likert scale survey was administered to participants at the beginning and end of the program, as well as one year after program completion. The instrument used in

these three instances of data collection included 16 questions relevant to the three types of TPB beliefs—behavioral beliefs (attitudes toward the behavior), normative beliefs (perceived attitudes of peers and respected figures toward the behavior), and control beliefs (perceived ability to perform the behavior)—and was divided into two sections. In the first section, on shellfish harvesting, questions asked about participants' perceptions of and experience with shellfish harvesting, perceptions of peers' views about shellfish harvesting, and sense of agency and behavioral intentions related to engaging in shellfish harvesting. For example, related to normative beliefs: "Most of the people who are important to me would approve of me participating in subsistence clam harvesting" (disagree – agree Likert scale). In the second section, on checking toxin levels using the SEATOR website, questions asked about participants' perceptions of this risk reduction behavior, perceptions of peers' views about checking toxin levels, and sense of agency and behavioral intentions related to checking toxin levels. For example, related to control beliefs: "I am confident that I can check the SEATOR website before clam harvesting" (disagree – agree Likert scale). In both sections, the last question asked about behavioral changes related to program learning and thus was relevant in only the post-program survey. Full survey response data is presented in appendix 2.

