2.5 Survey Data Analysis

2.5.1. Accounting for Missing Data

Missing data at the person-visit level were imputed for age (n missing = 6) and each of the questions (n missing = 9-20, depending on question), treating each person-visit as a separate observation. The predictor variables in the imputed model included all question responses and all regression model predictors: age, gender identity, Alaska Native identity, and site. We used listwise deletion, excluding cases from analysis if data was missing, for gender (n missing = 10), Alaska Native identity (n missing = 6), and pre-post-program differences (n missing = 9-15, depending on question). No site data was missing. We generated 80 imputed

datasets via multiple imputation by chained equations (Azur et al., 2011). Across our models, the largest average relative increase in variance (RVI) due to nonresponse was 0.44 and the largest fraction of missing information (FMI) was 0.55, suggesting that our analysis based on 80 imputed datasets was reasonable. Statistical analyses were conducted using STATA 18.0 M/P (StataCorp, 2023).

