2.5.2. Pre-Post-Program Changes in Theory of Planned Behavior Beliefs and Behavioral Intentions

To evaluate pre-post-program changes in beliefs and behavioral intentions related to shellfish harvesting, consumption, and risk reduction, we tested the association between pre- and post-program responses (i.e., the intervention effect). We included covariates for site (Sitka, Hoonah, and Juneau), age, Alaska Native identity (Alaska Native, non-Native), and gender identity (girls, boys, and nonbinary). To consider within person pre-post-program changes in TPB Beliefs and behavioral intentions, we used generalized estimating equation linear regression (GEE) to cluster pre-post measures (Liang & Zeger, 1986). We also evaluated differences in pre-post-program changes in TPB beliefs and behavioral intentions among the three participating communities and Alaska Native and gender identities using interacted models. Results of interacted models are presented in appendix 3.

We present individual participants' responses to the one year post-program survey as the number of participants in this follow-up survey was small. When we closed the study on July 31, 2024, only 7 participants had completed the program at least one year prior and were available for one year post-program recontact, having completed the program in either fall 2022 or spring 2023 semesters. These participants were all from Sitka. Of these 7 participants, 4 completed the follow-up survey. One year post-program survey responses are presented in appendix 4.

2.5.3. Relationships Between Changes in Theory of Planned Behavior Beliefs and Changes in Behavioral Intentions

To characterize TPB constructs most influential in shifting planned behaviors, we again used GEE to test the association between pre-post-program changes in TPB beliefs and pre-post-program changes in harvesting and exposure risk reduction behavioral intentions. Similar to the models we used to assess pre-post-program changes, we adjusted for site, age, Alaska Native identity, and gender identity. We also adjusted for changes in other TPB beliefs related to either shellfish harvesting or exposure risk reduction, depending on the behavioral intention outcome.

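### The primary outcome is the whole pre/post survey, and the methods text gives no primary item or score, significance level, number of models or multiplicity control, so the false-positive risk of the main analysis is undefined and probably above 5%

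*Combined protocol and SAP*

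**What the plan says.** All references are to the combined protocol and SAP.

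- **Primary outcome (2.2).** "Pre- and post-program surveys were the primary outcome measure of the clinical trial". Interviews and the one-year survey are secondary. No item, construct score or composite is singled out.
- **Instrument (2.4).** The survey "included 16 questions relevant to the three types of TPB beliefs" and "was divided into two sections", one on harvesting and one on checking toxin levels. In both, "the last question asked about behavioral changes related to program learning and thus was relevant in only the post-program survey".
- **Main analysis (2.5.2).** For beliefs and behavioral intentions, "we tested the association between pre- and post-program responses (i.e., the intervention effect"), using linear GEE with covariates. The number of such models is not given.
- **Further analyses.** Section 2.5.2 adds models with interactions by site, Alaska Native identity and gender: "Results of interacted models are presented in appendix 3". Section 2.5.3 regresses changes in intentions on changes in beliefs. Neither set is labelled confirmatory or exploratory.
- **Level of analysis.** It is not stated. The nearest evidence is in 2.5.1, where missing counts are given for "each of the questions (n missing = 9-20, depending on question") and for "pre-post-program differences (n missing = 9-15, depending on question").

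Nowhere does the supplied text give a significance level, sidedness, testing order or multiplicity adjustment.

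**The concern.** When an entire questionnaire is the primary outcome and its parts are tested separately, the primary analysis has several chances to show a change. Without a stated number of tests or threshold, a reader cannot judge how surprising one or two nominally significant changes would be. The text calls the pre-post contrast the intervention effect and ranks its measures as primary and secondary, so these results will be read as evidence that the program worked. If the tests were unadjusted, that evidence would be overstated. The size of the overstatement depends on how many tests were run and how strongly they correlate, and the text gives neither.

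**Working it through.** The plan gives no error rate or power figure, so there is nothing of its own to reproduce.

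**Inputs from the document**
- 16 questions, two of them post-program only (2.4): 16 − 2 = 14 questions with a pre-post contrast. This is a ceiling on question-level tests.
- Three types of belief plus intentions, in two sections (2.2, 2.4): (3 + 1) × 2 = 8 tests if the unit is construct by section. No scoring by construct is described, so 8 is a construction too.

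**Assumptions, none given in the document**
- One two-sided 0.05 test per outcome, unadjusted.
- No true change on any outcome.
- Correlation between test statistics as shown.

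**Independent tests:** 1 − 0.95^k.
- k = 14: 1 − 0.95^14 = 0.512.
- k = 8: 1 − 0.95^8 = 0.337.

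**Equal correlation r:** write each statistic as Z_j = √r·U + √(1−r)·E_j, with U and E_j independent standard normal. Then

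P(at least one) = 1 − ∫ [Φ((1.96 − √r·u)/√(1−r)) − Φ((−1.96 − √r·u)/√(1−r))]^k φ(u) du.

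| Correlation | 14 tests | 8 tests |
|---|---|---|
| 0 | 51% | 34% |
| 0.5 | 35% | 25% |
| 0.9 | 14% | 12% |
| 0.95 | 11% | 10% |
| 0.99 | 7% | 7% |
| 1 | 5% | 5% |

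**Two-section structure**, correlation 0.7 within a section and 0.3 between: Z_sj = √0.3·U + √0.4·V_s + √0.3·E_sj. Integrating over U and V_s gives 31.2% for 7 + 7 tests and 23.5% for 4 + 4. A simulation of 400,000 draws gave 31.1% and 23.4%.

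**Small-sample check.** If the 9 to 15 missing differences are out of 50, there are 50 − 15 = 35 to 50 − 9 = 41 pairs. Simulated paired t-tests at correlation 0.9 gave 14.3% to 14.7% (14 tests) and 12.1% (8 tests), close to the normal figures.

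**With Holm.** When all nulls are true, the familywise rate equals the rate of the first step, 0.05/k: 0.05/14 = 0.0036 and 0.05/8 = 0.0063. Putting these levels into the same formulas gives 4.9%, 3.7% and 1.4% for 14 tests, and 4.9%, 4.0% and 1.8% for 8 tests, at correlation 0, 0.5 and 0.9. These rates assume exact p-values.

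**The case against.** **The percentages are not properties of this plan.** They need a significance level, a number of tests, a global null and a correlation, none of which the document supplies. Independence is implausible for items answered by the same students in one instrument. This stands: 51% should not be the lead figure, and 0.9 is not a lower limit.

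**Question-level testing is inferred.** A reader might conclude that 14 separate primary tests were run. The text does not say so. Missing counts by question are equally compatible with imputing items and then scoring constructs, and the counts for differences may belong to 2.5.3, which models changes. Section 2.4 also mentions items on harvesting experience, which is neither a belief nor an intention and may not have been modelled. This stands as well. Dropping one such item would alter little: 1 − 0.95^13 = 0.487.

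**The appendices might give the count.** They might. The point is limited to the methods text, which is where the threshold and the family of tests belong.

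**Familywise control may be more than such a study needs.** It has one program group of 50 students and a mixed-methods design, no rule that any single changed item means success, and full survey responses in appendix 2. These features limit selective reporting, but they do not tell a reader how to weigh a p-value on the primary outcome. Nothing supplied labels the main pre-post tests exploratory.

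**Control beliefs could be taken as the primary construct**, since 2.2 says the program especially aimed at them. That sentence describes the design of the program and does not define an endpoint.

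**Conclusion.** The point holds as a gap with a real inferential consequence. The whole survey is primary, and the supplied methods text does not define the family of main tests, the threshold or any adjustment. With unadjusted 0.05 tests and no true change, a plausible two-section correlation puts the chance of at least one false change at about 31% for 14 tests or 23% to 24% for 8. The range runs from 51% or 34% under independence down to 5%, which is reached only at perfect correlation. All of these figures rest on the assumptions listed above.

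A reader might infer that the trial's false-positive rate is 51%, or that its reported changes are false. The document supports neither. It does not establish the number of tests or whether p-values were left unadjusted, and the calculation says nothing about whether any particular change is real.

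**What to change.** 1. In 2.5.2, state how many main pre-post models were fitted, on what unit (question or construct), and the threshold used.
2. Report Holm-adjusted p-values across that one family beside the unadjusted estimates and confidence intervals.
3. If the family and adjustment were not set before the data were seen, say that they are post hoc.
4. Describe the appendix 3 interaction models and the 2.5.3 change-on-change models as exploratory and outside the family.
5. Do not name a primary construct now. Section 2.5.2 records that the study has closed, and a choice made after the data are known would protect nothing.

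The cost is a few sentences and one column of p-values. Holm needs only the p-values pooled over the imputations, so no refitting should be needed if those are at hand, and no result is removed. Some single-item results may lose nominal significance, since the strictest step is 0.0036 for 14 tests or 0.0063 for 8. The loss of power cannot be computed, because 2.5.1 both imputes responses and deletes cases without giving the effective sample of the 2.5.2 models. Holm's control also depends on the GEE p-values being valid in a sample of about 50.

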2.3 Sample and Consent

Study participants were recruited from all middle school students (grades 6-8) in Blatchley Middle School in Sitka, Hoonah City School in Hoonah, and Dzantik'i Heeni Middle School in Juneau. The program enrolled 11 participants in Sitka, 20 in Hoonah, and 19 in Juneau for a total of 50 participants across communities. Research participation was not required to participate in the education program, and students opted into the survey and interview research components through a tiered informed consent process. Written consent was obtained from parents after information on research activities was shared, and verbal consent was obtained from participants before data collection activities. Of the 50 study participants, all consented to participate in the surveys and all but one consented to participate in the interviews. Participants in either or both research components were offered a \$10 cash card incentive for each lesson attended, with a total possible incentive of \$100 for attending all ten lessons. Incentives were used to encourage program participation and regular attendance.

2.4 Survey Design

A five-point (1-5) Likert scale survey was administered to participants at the beginning and end of the program, as well as one year after program completion. The instrument used in

these three instances of data collection included 16 questions relevant to the three types of TPB beliefs—behavioral beliefs (attitudes toward the behavior), normative beliefs (perceived attitudes of peers and respected figures toward the behavior), and control beliefs (perceived ability to perform the behavior)—and was divided into two sections. In the first section, on shellfish harvesting, questions asked about participants' perceptions of and experience with shellfish harvesting, perceptions of peers' views about shellfish harvesting, and sense of agency and behavioral intentions related to engaging in shellfish harvesting. For example, related to normative beliefs: "Most of the people who are important to me would approve of me participating in subsistence clam harvesting" (disagree – agree Likert scale). In the second section, on checking toxin levels using the SEATOR website, questions asked about participants' perceptions of this risk reduction behavior, perceptions of peers' views about checking toxin levels, and sense of agency and behavioral intentions related to checking toxin levels. For example, related to control beliefs: "I am confident that I can check the SEATOR website before clam harvesting" (disagree – agree Likert scale). In both sections, the last question asked about behavioral changes related to program learning and thus was relevant in only the post-program survey. Full survey response data is presented in appendix 2.

2.5 Survey Data Analysis

2.5.1. Accounting for Missing Data

Missing data at the person-visit level were imputed for age (n missing = 6) and each of the questions (n missing = 9-20, depending on question), treating each person-visit as a separate observation. The predictor variables in the imputed model included all question responses and all regression model predictors: age, gender identity, Alaska Native identity, and site. We used listwise deletion, excluding cases from analysis if data was missing, for gender (n missing = 10), Alaska Native identity (n missing = 6), and pre-post-program differences (n missing = 9-15, depending on question). No site data was missing. We generated 80 imputed

datasets via multiple imputation by chained equations (Azur et al., 2011). Across our models, the largest average relative increase in variance (RVI) due to nonresponse was 0.44 and the largest fraction of missing information (FMI) was 0.55, suggesting that our analysis based on 80 imputed datasets was reasonable. Statistical analyses were conducted using STATA 18.0 M/P (StataCorp, 2023).

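### Missing survey answers are imputed (2.5.1) without the same student's other survey, so any imputed answer used in the 2.5.2 GEE largely ignores the pre-post pairing that the model targets.

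*Combined protocol and SAP*

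**What the plan says.** Section 2.5.1 imputes age and each survey question by chained equations, "treating each person-visit as a separate observation". On predictors it says: "The predictor variables in the imputed model included all question responses and all regression model predictors: age, gender identity, Alaska Native identity, and site". It reports 9 to 20 missing answers per question. The same paragraph applies listwise deletion for missing gender (10), missing Alaska Native identity (6) and "pre-post-program differences (n missing = 9-15, depending on question"), without saying which models that covers.

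Section 2.5.2 describes the main analysis: "we tested the association between pre- and post-program responses (i.e., the intervention effect"). It names site, age, Alaska Native identity and gender identity as covariates, and to reflect change within a person, "we used generalized estimating equation linear regression (GEE) to cluster pre-post measures". Section 2.2 makes the pre- and post-program surveys the primary outcome measure. Section 2.5.3 relates changes in beliefs to changes in intentions.

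**The concern.** An imputation model should carry the relationships that the analysis model uses. Here the analysis rests on each student's two surveys being correlated. With one row per visit, the question responses available as predictors are naturally those in the same row. An imputed post answer is then tied to that student's pre answer only through the covariates and any same-visit answers the student gave. If the whole survey is missing, only the covariates remain.

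Two things are at stake. One is precision: the benefit of pairing is lost for the imputed part. The other, more important, is bias. If post-survey completion depends on the baseline answer, the observed baseline could correct for it, but this imputation does not use it.

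**Working it through.** **1. The plan's own figure.** Section 2.5.1 judges 80 imputed datasets reasonable for a largest FMI of 0.55. By the rule M ≥ 100 × FMI, 100 × 0.55 = 55 ≤ 80. Relative efficiency is 1/(1 + 0.55/80) = 0.993. The number is adequate, but it controls Monte Carlo error only. It does not show that the imputation model matches the paired analysis.

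**2. Inputs.** From the documents: 50 students (2.3) and 9–15 missing differences (2.5.1), which is 18–30% if out of 50. Assumed, because the documents do not give them: SD 1 at each visit, true change 0.40, pre-post correlation ρ = 0.3, 0.5 or 0.7, whole post surveys missing (15 unless stated), and covariates unrelated to the outcome. The simulation used normal outcomes, 30 imputations and 1,500 replicates, with the mean paired difference standing for the GEE time coefficient.

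**3. Pre/post term included, answers missing completely at random.** The estimate is unbiased. Mean SEs:

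| ρ | One row per visit + pre/post term | One row per student | Random-intercept model |
|---|---|---|---|
| 0.3 | 0.203 | 0.203 | 0.194 |
| 0.5 | 0.189 | 0.176 | 0.165 |
| 0.7 | 0.173 | 0.139 | 0.127 |

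First column over second: 1.00, 1.07, 1.24.

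Hand check, without covariates:
- Row-per-visit imputation keeps only 35/50 = 0.7 of the covariance. Its variance is 2(1 − 0.7ρ)/50 + (1/35 − 1/50), giving SEs of 0.200, 0.186 and 0.170.
- A model using the pairing has variance 2(1 − ρ)/50 + (1 − ρ²)(1/35 − 1/50), giving 0.189, 0.163 and 0.128, close to the random-intercept column.
- Paired imputation falls short of that because it estimates the covariate terms from only 35 complete rows.

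The loss is smaller in other settings:
- 9 missing: 0.188/0.186 = 1.01, 0.169/0.160 = 1.06, 0.148/0.125 = 1.18.
- Single skipped items (four same-visit items, correlation 0.5): −3 to −1%, +1 to 2%, +9 to 11%.
- 40 students (7 or 12 missing): −2 to 0%, +5 to 6%, +17 to 22%. With 34 students (6 or 10 missing): −4 to −1%, +3 to 4%, +16 to 19%.

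The smaller samples reflect deletion for gender and Alaska Native identity: 50 − 16 = 34 to 50 − 10 = 40 if the counts are students. If they are person-visits, 50 − 8 = 42 to 50 − 5 = 45 remain. These figures assume that deleted students were no likelier to have missed a survey.

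**4. Pre/post term included, lower-baseline students more often missing the post survey.** The approximate estimate is 0.40 + ρ × gap × share missing, where gap is the baseline difference between students with and without a post survey and the share is 15/50 = 0.30.
- Gap 0.45 SD: formula 0.44, 0.47, 0.49; simulated 0.43, 0.46, 0.48.
- Gap 0.81 SD: formula 0.47, 0.52, 0.57; simulated 0.46, 0.50, 0.55.

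The formula runs slightly high because covariates recover a little of the pairing. Paired imputation and the random-intercept model both give about 0.40. If higher-baseline students are the ones missing, the change is understated.

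**5. No pre/post term.** Let p = observed post/(observed pre + observed post). If answers are missing completely at random, the share of the true change retained is (observed post + p × missing post − p × missing pre)/50.
- 9 post missing: p = 41/91, (41 + 4.05)/50 = 0.90.
- 15 post missing: p = 35/85, (35 + 6.18)/50 = 0.82.
- 5 pre and 15 post missing: p = 35/80, (35 + 6.56 − 2.19)/50 = 0.79.
- 4.5 pre and 4.5 post on average: p = 0.5, 45.5/50 = 0.91.

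Under the baseline-dependent missingness of step 4, the two biases partly offset. Estimates of 0.40 are 0.35, 0.37, 0.39 (gap 0.45) and 0.37, 0.41, 0.45 (gap 0.81).

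**6. Effect of a paired imputation on 2.5.3.** Predicting each answer only from the same question at the other visit plus covariates leaves out the other questions. With same-visit correlation 0.5, surveys missing completely at random and a true slope between changes of 0.50, that imputation gives about 0.40–0.42 with 9 missing and 0.36–0.38 with 15. Complete pairs give about 0.50.

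**The case against.** The GEE itself respects pairing, and observed pairs are untouched. Covariates and same-visit answers also carry some of the between-student correlation. This stands, and is why the claim is only that pairing is largely ignored, and only for imputed answers.

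The link to the primary result is not stated. Section 2.5.1 both imputes answers and deletes missing differences. Imputation in 2.5.2 and deletion in 2.5.3 is the natural reading, not an explicit one. The reported average RVI of up to 0.44 and FMI of up to 0.55 would be surprising from six imputed ages alone, which suggests, without proving, that imputed answers carried weight in some models.

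A pre/post term may have been used. Section 2.5.1 claims to include every regression predictor, and pre/post is the main one in 2.5.2, yet the list after the colon gives only the four covariates. A reader might infer that the term was left out; the text does not establish that. The pairing is lost either way.

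The size is unknown. With a pre/post term, data missing completely at random and a correlation near 0.3, the harm is close to nil, and at higher correlations it is conservative. This stands. Missing counts by visit may also be in appendix 2, which is not in the documents reviewed.

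**Conclusion.** The concern holds as a mismatch between the imputation in 2.5.1 and the paired analysis in 2.5.2, and it should be fixed. Confidence is high for the omission and moderate at most for its effect.

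Under the stated assumptions, the cost ranges from nothing to an SE about 24% too large when a pre/post term was used and data are missing completely at random. It becomes an overstatement, to about 0.43–0.55 for a true 0.40, when lower-baseline students drop out.

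Two stronger readings are not supported. One is that the reported program effect is inflated: that needs a missingness pattern which the documents do not describe. The other is that the effect is shrunk to 79–91% of the truth: that needs both an absent pre/post term and data missing completely at random. With baseline-dependent missingness and no pre/post term, the result is about 0.35–0.45 for a true 0.40, so even the direction is unknown.

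**What to change.** For 2.5.2, fit a linear mixed model with a student random intercept, a pre/post term and the stated covariates to all observed answers, imputing only the 6 missing ages. Because the study is closed, label this post hoc and show it beside the existing results.

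As a secondary check, impute with one row per student, predicting each answer from the same question at the other visit plus the covariates. For single skipped items, also allow up to two pre-listed same-construct items from that visit. Check stability: in one simulation run with 40 students and 9 missing, near-empty site cells raised the mean SE to 0.91, against a usual 0.21–0.23. Do not carry this imputation into 2.5.3, for the reason in step 6; keep complete pairs there.

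Suggested wording: *Pre-post change was re-estimated post hoc with a linear mixed model (student random intercept) on all observed answers, adjusted for site, age, gender identity and Alaska Native identity; the models of 2.5.3 used complete pairs.* In the same paragraph, state whether the existing imputation held a pre/post term and which models used imputed answers.

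The cost is one extra script and a second set of results to report, with no new data. Neither method helps students with no answer at either visit.
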